**10.3.2 Safety Analyses**

All safety analyses (see Table 10.3.2-1) will be performed on the treated population.

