**Table 4-1: Objectives and Endpoints**

Objectives	Endpoints
For Part 1, 2A, 2B Primary 

• To characterize the safety, tolerability, and DLTs and to determine the MTD/RP2D of BMS-986288 administered as monotherapy and in combination with nivolumab in participants with select advanced solid tumors

	

• Incidence of AEs, SAEs, AEs meeting protocol-defined DLT criteria, AEs leading to discontinuation, and death.

For Part 1, 2A, 2B Secondary 

• To characterize the PK of BMS-986288 when administered alone and in combination with nivolumab

• To assess the preliminary efficacy of BMS-986288 alone and in combination with nivolumab in advanced solid tumors using RECIST v1.1

	

• Summary measures of PK parameters of BMS-986288

• ORR, DOR, PFS, and TTR per RECIST v1.1 by Investigator assessment

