### Sentinel Participant

During the Dose-Escalation Phase (Part 1), a staggered dosing (sentinel participant) approach will be used. The first participant to be dosed at Cycle 1 Day 1 of each dose level will be observed for 5 days, before additional participants (ie, Participant 2 onward in that cohort) receive study treatments in the same dose level.

Initially, 3 participants will be enrolled at the start of each cohort, in accordance with the sentinel participant approach cited above. However, to allow for any unforeseen discontinuations (such as disease progression) before the 5-week DLT period (35 days) is completed, an extra participant may be enrolled in each dose-escalation cohort. Therefore, there may be a total of 4 participants (3 + 1) at the start of each cohort, provided that the fourth participant is able to start dosing within

approximately 1 week of the third participant in the same dose-escalation cohort. Additional information on DLTs can be found in Section 5.1.2.1 and [Section 7.4.1](#).

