#### **7.4.1 Dose-limiting Toxicities**

For the purpose of guiding dose escalation, all AEs will be assessed and DLTs will be defined based on the incidence, intensity, and duration of the AEs for which no clear alternative cause is identified. The DLT period will be 5 weeks (35 days) in both BMS-986288 monotherapy and combination dose escalation (Part 1A and Part 1B). Any toxicities that occur beyond the DLT period will be accounted for in making final dose level decisions. Participants who have discontinued due to a DLT or who have received 2 doses of BMS-986288 monotherapy or in combination with nivolumab and have completed the 5-week DLT period will be considered as DLT-evaluable participants. Participants who withdraw from the study during the DLT evaluation period or have received less than 2 doses for reasons other than a DLT in both monotherapy and combination therapy will not be considered as DLT-evaluable participants and may be replaced with a new participant at the same dose level. Participants who are dose delayed during the DLT evaluation period for reasons other than a DLT in both monotherapy and combination therapy will be considered as DLT-evaluable participants if they received at least 2 doses of therapy within 8 weeks.

For the purpose of participant management, any drug related AE that meets DLT criteria, regardless of the cycle or cohort in which it occurs, will lead to discontinuation of study treatment.

AEs will be graded according to the NCI CTCAE v5.0.

Continuous evaluation of toxicity events in the [REDACTED] Evaluation of BMS-986288 [REDACTED] and BMS-986288 Cohort Expansion Combination Therapy (Part 2) will be performed. If at any time, the aggregate rate of treatment-related toxicities meeting DLT criteria in a BMS-986288 containing cohort exceeds 33% across patients treated in a cohort, the findings will be discussed with the Investigators and further enrollment may be interrupted. If a cohort is discontinued due to toxicity, a new cohort at a previously tested alternative dose level which was found to be safe in Part 1A or Part 1B may be considered based on the aggregate safety experience and in consultation and agreement between Investigators and Sponsor. An alternative dose or administration schedule may also be initiated in a specific [REDACTED] or Part 2 cohort upon

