**Table 10.2-1: Populations for Analyses**

Population	Description
Enrolled	All participants who sign informed consent and are registered into the Interactive Response Technology (IRT)
Treated	All participants who take at least 1 dose of study treatment
Response-evaluable	All treated participants with measurable disease at baseline and 1 of the following: (a) at least 1 post baseline tumor assessment; (b) clinical progression; and (c) death
Pharmacokinetic	All treated participants who have evaluable concentration-time data
Immunogenicity	All treated participants who have baseline and at least 1 post-baseline pre-infusion immunogenicity assessment
Biomarker	All treated participants with available biomarker data
Clinical outcomes population (Part 2A and Part 2B only)	All treated participants who have a valid clinical outcomes assessment at baseline and at least 1 matched on-treatment post-baseline assessment

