**Table 10.3.2-1: Safety - Statistical Analyses**

Endpoint	Statistical Analysis Methods
Incidence of DLTs, AEs, SAEs, AEs leading to discontinuation, and death. AEs will be graded according to CTCAE v5.0.	DLT rate by dose level, frequency distribution of treated participants with AE using the worst CTC grade. Participants will only be counted (1) once at the PT level, (2) once at the system organ class level, and (3) once in the 'total participant' row at their worst CTC grade, regardless of system organ class or PT
Laboratory abnormalities. Laboratory values will be graded according to CTCAE v5.0.	Laboratory shift table using the worst CTC grade on-treatment per participant

Abbreviations: AE = adverse event; DLT = dose-limiting toxicity; CTC = common terminology criteria; CTCAE = common terminology criteria for adverse events; PT = preferred term; SAE = serious adverse event.

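### The reported Part 1 DLT rate is set on all treated participants, so early drop-outs whom Section 7.4.1 calls not DLT-evaluable dilute it

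*Combined protocol and SAP*

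**What the plan says.** Table 4-1 makes this the primary endpoint for Parts 1, 2A and 2B: "Incidence of AEs, SAEs, AEs meeting protocol-defined DLT criteria, AEs leading to discontinuation, and death". Section 10.3.2 fixes the analysis set without exception: "All safety analyses (see Table 10.3.2-1) will be performed on the treated population". The method entry in Table 10.3.2-1 begins "DLT rate by dose level, frequency distribution of treated participants with AE using the worst CTC grade" and gives the DLT rate no denominator of its own, so the general sentence supplies it. Table 10.2-1 defines the treated population as "All participants who take at least 1 dose of study treatment". That table also has response-evaluable, pharmacokinetic, immunogenicity, biomarker and clinical-outcomes sets, but no DLT-evaluable set.

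Section 7.4.1 does define who is DLT-evaluable in Parts 1A and 1B. Participants who discontinue because of a DLT qualify. So do those who receive two doses and "have completed the 5-week DLT period will be considered as DLT-evaluable participants". Participants delayed for reasons other than a DLT still count if they receive at least two doses within 8 weeks. Those who withdraw during the DLT period, or receive fewer than two doses, for reasons other than a DLT "will not be considered as DLT-evaluable participants and may be replaced with a new participant at the same dose level".

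Sections 5.2, 10.1.1 and 10.1.2 express Part 1 numbers in DLT-evaluable participants. Section 10.3.8.1 treats every treated participant as evaluable, but only for Part 2.

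**The concern.** Sections 7.4.1 and 10.3.2 give different answers to who belongs in the Part 1 DLT-rate denominator. A participant who progresses and leaves in week 2 after one dose is set aside and replaced under Section 7.4.1, then counted in the DLT table under Section 10.3.2 as someone without a DLT. That participant was only partly observed over the 5-week window.

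The plan expects such cases. The Sentinel Participant text in Section 5.1.2 says that, to cover discontinuations before day 35, "an extra participant may be enrolled in each dose-escalation cohort".

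At stake is the reported DLT rate by dose level in a first-in-human study whose primary objective includes finding the MTD or RP2D. It would be lower than the rate among the participants on whom dose finding was based, and a reader could not reconcile the two from the table.

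**Working it through.** **The plan's own figure.** No Part 1 DLT rate is stated. The one DLT figure that can be recomputed is the final Part 2 monitoring boundary in Section 10.3.8.1: 16 of 40, from a Beta(0.5, 0.5) prior and a posterior probability above 0.80 that the rate exceeds 33%.

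- 15 of 40: posterior Beta(15.5, 25.5), P(rate > 0.33) = 0.731
- 16 of 40: posterior Beta(16.5, 24.5), P(rate > 0.33) = 0.827

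The smallest count above 0.80 is 16, so the plan's figure is reproduced. It is a Part 2 figure and does not test the Part 1 point.

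**Inputs for Part 1.**

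- d: DLTs in the 5-week period
- E: DLT-evaluable participants at the dose level (Section 7.4.1)
- x: treated participants at that level who are not DLT-evaluable. This number is not in the documents; I assume 1 to 3.
- Cohort sizes of 3, with one optional extra (Section 5.1.2), and 6, the minimum at the MTD (Sections 10.1.1 and 10.1.2)

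**Formula.** The rate on evaluable participants is d/E. A participant counted in x left for a reason other than a DLT, so adds 1 to the denominator and 0 to the numerator. The rate on treated participants is therefore d/(E+x) = (d/E) × E/(E+x).

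**Results.**

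| d/E | x = 0 | x = 1 | x = 2 | x = 3 |
|---|---|---|---|---|
| 2/6 | 33.3% | 2/7 = 28.6% | 2/8 = 25.0% | 2/9 = 22.2% |
| 1/3 | 33.3% | 1/4 = 25.0% | – | – |

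The 1/3 row is a 3+1 cohort in which one of the four is not evaluable. If the fourth participant completes the period, x = 0 and there is no dilution.

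Expressed as a share f of treated participants who are not evaluable (also assumed), the factor is 1 − f. A 33% rate would be reported as:

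- f = 10%: 0.33 × 0.90 = 29.7%
- f = 20%: 0.33 × 0.80 = 26.4%
- f = 25%: 0.33 × 0.75 = 24.8%

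**A second group.** Part 1B participants with NSCLC join a dose level only after it has been found tolerable (Sections 5.4.1 and 6.1), so they are outside the initial DLT assessment. They are still treated participants and also change the denominator. The direction depends on their own events, so they are left out of the figures above.

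**The case against.** The strongest reply has five parts.

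- **Dose decisions.** A reader might infer that escalation or the MTD is biased. The documents do not support that. Sections 10.1.1 and 10.1.2 describe the BLRM and BLRM-copula in terms of DLT-evaluable participants and DLT-period data, and Section 10.3.2 governs reported tables. Nor would the report necessarily contradict the dose decision: the final MTD/RP2D also rests on overall clinical assessment, and late events meeting DLT criteria may enter the model. A descriptive rate need not equal the model estimate even with the right denominator.
- **The 33% limit.** It is tempting to say that moving from 33.3% to 25% crosses the plan's limit. In Part 1 that limit bounds a modelled rate: the posterior probability of a DLT rate of 33% or more may not exceed 35%. It is not a cutoff for one cohort's observed proportion, so no Part 1 rule is triggered.
- **Partial observation.** Saying the excluded participants were never observed for a DLT would be too strong. Some may have had one dose and several weeks of follow-up.
- **Which events count.** The Table 4-1 endpoint does not restrict events to 5 weeks. For events meeting DLT criteria at any time, the treated population is a coherent denominator. The downward bias is certain only for the 5-week rate.
- **Deferral.** Section 10.3 calls itself a summary, with a statistical analysis plan to be finalized before database lock. That plan could supply the missing link.

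The first four stand and limit the point. The fifth does not remove it. Section 10.3.2 states a rule that covers the DLT rate; it does not leave the denominator open. An analysis plan written from it would carry the same conflict.

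**Conclusion.** The point holds for the reported Part 1 DLT rate over the 5-week period. Section 10.3.2 assigns it to the treated population, Section 7.4.1 excludes early non-DLT drop-outs from DLT evaluation, and nothing in the documents restores an evaluable denominator for Part 1. The reported rate is then too low by the factor E/(E+x).

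With x assumed to be 1 to 3, an observed 33.3% in 6 evaluable participants would appear as between 28.6% and 22.2%. The true size depends on x, which the documents do not give, and is nil where every treated participant is evaluable. The conclusion also assumes that the tabulated rate means DLTs within the 5-week window, which Table 10.3.2-1 does not say.

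The consequence is a primary-endpoint summary that understates the rate and does not match the data used for dose finding. It should be corrected, but it gives no ground for saying that dosing decisions are wrong.

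**What to change.** 1. Add to Table 10.2-1 a DLT-evaluable population for Part 1 only, using the Section 7.4.1 definition, including its provision for delayed doses.
2. State in Section 10.3.2 that the Part 1 DLT rate by dose level counts events in the 5-week DLT period and uses this population.
3. Keep the treated population for all other safety analyses, for AEs meeting DLT criteria at any time, and for Part 2, including the Section 10.3.8.1 monitoring and Part 2C.

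The restriction to Part 1 matters. Section 10.3.8.1 counts every treated Part 2 participant as evaluable. The Section 7.4.1 definition also asks for doses of BMS-986288, which does not fit the regorafenib arm of Part 2C (Arm D).

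The cost is a few lines of wording, repeated in the statistical analysis plan. No new data are needed.

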**Table 10.3.2-1: Safety - Statistical Analyses**

Endpoint	Statistical Analysis Methods
Incidence of DLTs, AEs, SAEs, AEs leading to discontinuation, and death. AEs will be graded according to CTCAE v5.0.	DLT rate by dose level, frequency distribution of treated participants with AE using the worst CTC grade. Participants will only be counted (1) once at the PT level, (2) once at the system organ class level, and (3) once in the 'total participant' row at their worst CTC grade, regardless of system organ class or PT
Laboratory abnormalities. Laboratory values will be graded according to CTCAE v5.0.	Laboratory shift table using the worst CTC grade on-treatment per participant

Abbreviations: AE = adverse event; DLT = dose-limiting toxicity; CTC = common terminology criteria; CTCAE = common terminology criteria for adverse events; PT = preferred term; SAE = serious adverse event.

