dose level will be based on the PK data obtained from the [REDACTED] dosing schedule and will not exceed a dose equivalent determined to be tolerable. Implementation of these alternative dose schedules will not include the addition of new procedures and will be documented in a note to file or administrative letter.

 For participants who transition from regorafenib (Part 2C Arm D) to receive BMS-986288 in combination with nivolumab, PK, biomarker, physical examinations, vital sign measurements, and clinical laboratory evaluations will be performed on the same schedule of combination therapy starting at C1D1 and moving forward. A biomarker sample should be collected at the time of initial documented disease progression as the requirement at EOT visit and will be treated as screening sample in Part 2C Arm Z. Efficacy and safety data obtained after starting the combination therapy will be analyzed separately; however, safety data from these participants will be considered among the totality of data used for safety evaluation.

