**Table 2-3: Follow-up Procedural Outline for All Study Parts**

Procedure	Safety Follow-up (relative to the last dose of study treatment or date of discontinuation, whichever is later)			Imaging Follow-up	Survival Follow-up (assessed every 12 weeks for 2 years from EOT)	Notes
	Follow-up 1 30 Days (± 7 Days)	Follow-up 2 60 Days (± 7 Days)	Follow-up 3 100 Days (± 7 Days)			
Safety Assessments						
PE	X	X	X			
Vital Signs	X	X	X			Includes body temperature, seated/supine blood pressure, and heart rate.
Laboratory Tests	X	X	X			Laboratory tests also as clinically indicated. See laboratory assessments in Section 9.4.5 and Table 9.4.5-1 .
Urinalysis	As clinically indicated (see Section 9.4.5 ).					
Pregnancy Test	X	X	X			For WOCBP, serum/urine pregnancy test is to be performed (urine pregnancy test: minimum sensitivity 25 IU/L or equivalent units of hCG; see Section 9.2.5 ).
Adverse Event Reporting and Concomitant Medication Assessments						
Monitor for Non-SAEs	X	X	X		See Notes	Nonserious AEs will be collected continuously starting with the first dose of study treatment and through 100 days after last dose of study treatment (see Appendix 3 and Section 9.2 ).
Monitor for SAEs	X	X	X		See Notes	All SAEs must be collected continuously from the date of the participant's written consent until 100 days after last dose of study treatment (see Appendix 3 and Section 9.2).
Monitor for SARS-CoV-2-related	X	X			See Notes	Participants will be followed for all SAEs and all AEs (SAEs and nonserious AEs) associated with confirmed or suspected

**Table 2-3:** Follow-up Procedural Outline for All Study Parts

Procedure	Safety Follow-up (relative to the last dose of study treatment or date of discontinuation, whichever is later)			Imaging Follow-up	Survival Follow-up (assessed every 12 weeks for 2 years from EOT)	Notes
	Follow-up 1 30 Days (± 7 Days)	Follow-up 2 60 Days (± 7 Days)	Follow-up 3 100 Days (± 7 Days)			
Nonserious AEs and SAEs						SARS-CoV-2 infection until resolution, the condition stabilizes, the event is otherwise explained, the event is deemed irreversible, the participant is lost to follow-up (as defined in Section 8.3 ), or for suspected cases, until SARS-CoV-2 infection is ruled-out.
Concomitant Medications	X	X	X			
Sample Collection						

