**Table 4-1: Objectives and Endpoints**

Objectives	Endpoints

 
To measure [REDACTED], and assess [REDACTED] change over time and in association with response
 
	
 
Mean EQ-5D-5L utility index scores and EQ-5D-VAS scores and change from baseline scores
 
Summary measures of [REDACTED] and correlation/ measure of association of anti-tumor activity and change (or % change) from baseline in [REDACTED]
 

For Part 2C Primary 
 
To compare the efficacy of BMS-986288 in combination with nivolumab vs regorafenib in the 3L/4L MSS CRC setting.
 
	
 
ORR per RECIST v1.1 by BICR
 

For Part 2C Secondary 
 
To compare the efficacy of BMS-986288 in combination with nivolumab vs regorafenib in the 3L/4L MSS CRC setting
 
To characterize the safety and tolerability of BMS-986288 in combination with nivolumab vs regorafenib in the 3L/4L MSS CRC setting
 
	
 
DOR and PFS per RECIST v1.1 by BICR, and OS
 
ORR, DOR, and PFS per RECIST v1.1 by Investigator assessment
 
Incidence of AEs, SAEs, AEs meeting protocol-defined DLT criteria, AEs leading to discontinuation, and death
 

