#### **5.1.5 Criteria for Transition From Regorafenib (Part 2C Arm D) to BMS-986288 in Combination with Nivolumab**

Participants in the regorafenib arm (Part 2C Arm D) may receive BMS-9864288 in combination with nivolumab provided that the criteria below are met:

- The participant has PD per RECIST v1.1 (as assessed by BICR).
- The participant has completed at least 2 cycles of regorafenib.
- At least █ days have elapsed since the last dose of regorafenib.
- AEs have returned to  $\leq$  Grade 1 or baseline, except clinically insignificant laboratory values which must have returned to  $\leq$  Grade 2 or to baseline.
- Provided participants still meet physical and laboratory test findings inclusion criteria (see [Section 6.1](#) Inclusion Criterion 3)).
- Participant does not have any condition, including active or uncontrolled infection, or the presence of laboratory abnormalities, which places the participant at unacceptable risk.

- Participant provides written informed consent prior to receiving additional treatment.

For Part 2C Arm D participants who elect to crossover to Part 2C Arm Z to receive BMS-986288 in combination with nivolumab, a collection [REDACTED] is mandatory in order to provide pre-treatment information. These participants may continue treatment at the next scheduled treatment visit and will be followed on study for up to 2 years from the last dose of study intervention.

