## **Part 2C**

Part 2C is a randomized, open-label study with 2 treatment arms, nivolumab in combination with BMS-986288 (Arm C) versus regorafenib (Arm D). Once enrolled in IRT, participants who have met all eligibility criteria for Part 2C will be randomized in a 2:1 ratio to nivolumab in combination with BMS-986288 (Arm C) or regorafenib (Arm D) and stratified by liver metastases status. Participants in Part 2C Arm D receiving regorafenib will have the option to transition to BMS-986288 in combination with nivolumab (Part 2C Arm Z) after BICR-assessed progression.

An additional dose of BMS-986288 █ mg or █ mg) in combination with nivolumab may be opened in Part 2C (as Arm E). This additional dose level will not be randomized with Arm C and Arm D.

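### Part 2C safety against regorafenib is planned as crude incidence only, although the regorafenib observation window closes at crossover, so the table can overstate the combination's relative toxicity

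*Combined protocol and SAP*

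**What the plan says.** Table 4-1 lists as a Part 2C secondary objective: "To characterize the safety and tolerability of BMS-986288 in combination with nivolumab vs regorafenib in the 3L/4L MSS CRC setting". The endpoint is the incidence of AEs, SAEs, AEs meeting DLT criteria, AEs leading to discontinuation, and death.

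Section 10.3.2 states that all safety analyses "will be performed on the treated population". For AEs, Table 10.3.2-1 gives a DLT rate by dose level and a "frequency distribution of treated participants with AE using the worst CTC grade", each participant counting once per level. Section 10 names no person-time, exposure-adjusted or time-to-event AE analysis.

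On collection, Table 2-3 has: "Nonserious AEs will be collected continuously starting with the first dose of study treatment and through 100 days after last dose of study treatment". Section 5.1.3.1 keeps the Day 30, 60 and 100 safety visits in place even if new anti-cancer therapy starts.

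Crossover exists only in Arm D (Sections 5.1.5 and 7.2). It is optional, follows progression by blinded central review, and has further conditions, among them: "The participant has completed at least 2 cycles of regorafenib". For those who cross over, a footnote to Table 2-2 says: "Efficacy and safety data obtained after starting the combination therapy will be analyzed separately". The same footnote keeps these data within the totality used for safety evaluation.

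**The concern.** A proportion with at least one event depends on how long people are watched. Every Arm C participant is followed through treatment plus 100 days. An Arm D participant who does not cross over is followed in the same way. For one who does, the regorafenib record stops at the first combination dose, and the 100-day tail shrinks to the regorafenib-free interval. The cut is built into one arm only.

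Treatment time may differ as well. The combination is capped at 2 years but can continue beyond initial progression (Sections 5.1.4, 5.1.4.1 and 5.4.6). Regorafenib has no cap but runs until progression (Sections 5.1.2 and 5.4.6).

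At stake is the benefit-risk reading of Part 2C: for events that accrue over time, two equally toxic regimens would not produce equal crude percentages. AEs leading to discontinuation are a partial exception. They arise on treatment, so the loss of the tail does not touch them, although unequal treatment time does.

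**Working it through.** The plan gives no figure for this comparison, so there is nothing to reproduce. The check asks what crude ratio (Arm C over Arm D) appears when the true AE rates are identical.

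**Inputs from the protocol.** Follow-up of 100 days after last dose (Table 2-3). At least 2 regorafenib cycles before crossover (Section 5.1.5) of 28 days each (Section 7.1), which is 56 days.

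**Assumptions.** Washout 14 days, range 7 to 28 (redacted in Section 5.1.5). Crossover share *c* from 0 to 100% (not given). Treatment durations (not given). Constant event rate λ, the same in both arms.

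**Model.** Incidence over a window W is 1 − exp(−λW). With 56 days of treatment in both arms:
- Arm C, and Arm D without crossover: W = 56 + 100 = 156 days.
- Arm D with crossover: W = 56 + 14 = 70 days.

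For a rare AE the ratio tends to the ratio of mean windows, 156 / [156(1 − c) + 70c]. At c = 50% this is 156/113 = 1.38.

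| Equal 56-day treatment | c = 0 | 30% | 50% | 70% | 100% |
|---|---|---|---|---|---|
| Rare AE | 1.00 | 1.20 | 1.38 | 1.63 | 2.23 |
| Arm C incidence 50% | 1.00 | 1.16 | 1.30 | 1.48 | 1.87 |
| Arm C incidence 80% | 1.00 | 1.12 | 1.22 | 1.33 | 1.56 |

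The rare-AE ratio reaches 2 when 156 − 86c = 78, so at c = 91%.

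**Washout.** At 7 days the rare-AE ratio is 1.22 to 1.72 for c = 30 to 70%. At 28 days it is 1.16 to 1.48.

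**Longer treatment in both arms** (168 days each): 1.00 to 1.47 across c = 0 to 100%.

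**Unequal treatment, rare AE, 14-day washout:**
- Arm C 84 days, Arm D 56 days: 1.41 to 1.92 for c = 30 to 70%.
- Arm C 112, Arm D 56: 1.63 to 2.21 for c = 30 to 70%.
- Arm C 56, Arm D 112: 156/212 = 0.74 with no crossover, and 156/169 = 0.92 at c = 50%. The direction can reverse.

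**Variable durations** (exponential; crossover only after at least 56 days on regorafenib; 50 to 100% uptake among those eligible; rare AE): mean 80 days in both arms gives 1.13 to 1.31; Arm C 120 against Arm D 80 gives 1.38 to 1.60; 160 against 80 gives 1.63 to 1.88.

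**Early-onset events.** Section 5.5.1 reports a median onset of 4.6 weeks for Grade 2-4 immune-related AEs on ipilimumab. As an illustration, take exponential onset with that median among those who have an event, in both arms. The share captured by 156 days (22.3 weeks) is 1 − 2^(−22.3/4.6) = 96.5%, and by 70 days (10 weeks) 1 − 2^(−10/4.6) = 77.8%. The ratio is then 1.06, 1.11 and 1.16 at c = 30, 50 and 70%, and 1.24 at 100%.

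**Effect of the remedy.** With events per person-time at risk, equal constant rates give a ratio of 1.00 whatever the crossover share or treatment time.

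**The case against.** The strongest reply is that Section 10.3 is only a summary. The SAP is to be finalised before database lock, 100 days is a collection window, and Table 10.3.2-1 states no tabulation window for AEs. A shorter window or person-time rates are therefore not ruled out. This is fair as far as it goes: the gap is in the protocol-level plan. But the method that is stated is crude, and a future SAP does not change that.

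It can also be said that the safety objective is to characterise rather than compare, and that no formal safety test is planned. That limits the severity. The objective is still framed against regorafenib, and readers will set the two columns side by side.

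Three further points stand and limit the claim. First, Section 9.2.1 excuses SAE collection in any arm once new anti-neoplastic treatment starts, unless the event is suspected to be related. Arm C windows can therefore be cut too, and the asymmetry is narrower for SAEs; nonserious AEs have no such exception. Second, post-crossover data are separated, not discarded, although that does not make Arms C and D comparable. Third, a constant rate fits early immune-related events poorly, and the illustration above shows a much smaller effect for them.

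A reader might infer that twofold is the limit, or the expected size, of the distortion. The documents support neither. They give no crossover share or treatment durations, and the washout is redacted. Twofold needs about 91% crossover under equal 56-day treatment, while much longer combination treatment can take the ratio past it. A reader might also infer that the combination will be given for longer. No section says so, and regorafenib has no cap.

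**Conclusion.** The concern holds in a limited form. As written, the plan sets crude incidence against regorafenib while closing the observation window at crossover in Arm D alone. This can overstate the combination's relative toxicity. It does not follow that it will: longer regorafenib treatment could offset or reverse the bias.

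Under equal constant rates, equal 56-day treatment and a 14-day washout, the spurious ratio for a rare AE is about 1.2 to 1.6 at 30 to 70% crossover. It is nearer 1.1 to 1.3 for an AE seen in 80% of Arm C, and about 1.1 to 1.2 for events with early onset. The size rests on assumptions about crossover, washout and duration that the documents do not settle, so it should be quoted as a range. This is a worthwhile and inexpensive improvement to a secondary analysis. It does not affect the primary endpoint.

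**What to change.** For Part 2C, keep the crude worst-grade table as a per-arm description, state its window, and add to Table 10.3.2-1 and the SAP:

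1. Exposure-adjusted incidence rates: first events divided by person-time at risk, with Arm D time ending at the first combination dose.
2. A between-arm table over a window of fixed, equal length from first dose. The first 56 days is a natural choice and is essentially free of crossover, because 2 completed 28-day cycles are required first. Alternatively, report cumulative incidence of first event at fixed times, censored at crossover.

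A window defined only by rule, such as first dose to 30 days after last dose or crossover, would not serve. With 84 days of combination and 56 of regorafenib it still compares 84 + 30 = 114 days with 56 + 14 = 70, a ratio of 1.63 for a rare AE. It would also omit later immune-mediated events, although Appendix 4 counts relevant exposure on the combination to 125 days after treatment.

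The cost is a few extra tables from dates and events already collected, with no change to treatment, visits or sample size. The drawback is that person-time rates can dilute early-onset events in the longer-exposed arm and so flatter it. That is why the fixed-window table should be shown beside them.
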